Title: No Post Intubation Laryngeal Symptoms (No-PILS)

NCT05383417

Date: April 12, 2023

Study Protocol

Description:

Single center randomized controlled trial with 100 subjects who will be intubated for already planned surgeries. The participants will be randomized into the control group or the clip group. The clip group will have a small clip (the endotracheal tube support device, also known as EndoClip) placed on the endotracheal tube to reduce the pressure on the vocal cords and larynx. This endotracheal tube support device is made from a FDA approved biocompatible material. The University of California San Diego Institutional Review Board ("IRB") approved this study (IRB #800842).

The control group subjects will undergo their planned procedure with no intervention during intubation. The clip group will undergo their planned procedure as normal but with the EndoClip placed on the endotracheal tube by the assigned anesthesia attending physician or trained clinician. The EndoClip is placed once the tube is secured and the ventilator circuit is connected. While extubating the patient, the endotracheal tube will be removed with the EndoClip attached and a picture of the tube will be taken to record the clip location.

Before the planned procedure, the investigators will survey the participants to get a baseline for any pre-existing laryngeal symptoms. The same survey will be administered after the procedure when the participants are awake and alert ('Day 0'), 24 hours ('Day 1'), 48 hours ('Day 2'), and 1 week ('Day 7') after the procedure. The survey will ask the participant to indicate "yes" or "no" for whether they are experiencing a sore throat, throat pain, oral pain, difficulty speaking, difficulty swallowing, changes in their voice, pain while speaking, and pain while swallowing. If they have indicated "yes" for any of the symptoms, the participants will also be asked to rate the severity on scale from 0 (no pain/difficulty) to 10 (severe pain/difficulty). If they indicate "no", this will be considered a score of 0 for the respective outcome variable.

Other data points will also be collected in this study that are related to the intubation and participant's airway. The investigators will record the total time of the procedure and the length of time the clip is placed on the endotracheal tube. For each participant in the clip group, the investigators will also record the time it takes to place the clip on the endotracheal tube. Each participant's airway will be evaluated, and the investigators will record the thyromental distance, Mallampati score, history of difficult intubation, and the size of the endotracheal tube used. Lastly, data from each participant's intubation will be collected including number of attempts before successful intubation, incidence of dental injury, incidence of lip injury, laryngeal view on Cormack-Lehane scale, and any noted trauma upon extubation.

At any point during the study, the participant can withdraw from the study. All study participants will be identified according to a number assigned at the beginning of the study, using key code.

Study Design:

Study Type:	Interventional
Primary Purpose:	Prevention
Study Phase:	Closed
Interventional Study Model:	Parallel Assignment

	2 arm parallel trial where one group will receive the endotracheal tube clip (EndoClip) during general endotracheal anesthesia and the other group will not (control)
Number of Arms:	2
Masking:	Double (Participant, Outcomes Assessor) Patient will not be aware of their treatment arm. Investigator and Care Provider will be aware of treatment arm but data analysis (outcomes assessor) will be blinded to treatment groups.
Allocation:	Randomized
Enrollment:	100 [Actual]

Arms and Interventions:

Arms	Assigned Interventions
Experimental: EndoClip Clip applied to endotracheal tube.	Device: EndoClip Clip attached to mid portion of the endotracheal tube. Other Names: 
• Endotracheal tube clip• Endotracheal tube support clop• Endotracheal tube support device
No Intervention: No Clip No clip applied to endotracheal tube.	

Outcome Measures:

Primary Outcome Measure:

1. Sore throat on a scale from 0 (no sore throat) to 10 (worst possible sore throat). Subjects will indicate whether they are experiencing a sore throat or throat discomfort on a questionnaire. If they indicate 'yes' they will be asked to mark the severity of their symptoms on a scale ranging from 0 (no sore throat) to 10 (worst possible sore throat). Participants will be asked to report on their symptoms prior to intubation, after intubation on the day of discharge, 24 hours after intubation, 48 hours after intubation, and 1 week after intubation.
[Time Frame: Baseline to 1 week after intervention]
2. Change in voice on a scale from 0 (no voice change) to 10 (most severe voice change). Subjects will indicate whether they are experiencing a change in voice (i.e. deep and/or hoarse voice, worse than their usual voice quality) on a questionnaire. If they indicate 'yes' they will be asked to mark the severity of their symptoms on a scale ranging from 0 (no voice change) to 10 (most severe voice change). Participants will be asked to report

on their symptoms prior to intubation, after intubation on the day of discharge, 24 hours after intubation, 48 hours after intubation, and 1 week after intubation.

[Time Frame: Baseline to 1 week after intervention]

3. Difficulty swallowing on a scale from 0 (no difficulty swallowing) to 10 (complete inability to swallow). Subjects will indicate whether they are experiencing difficulty swallowing on a questionnaire. If they indicate 'yes' they will be asked to mark the severity of their symptoms on a scale ranging from 0 (no difficulty swallowing) to 10 (complete inability to swallow). Participants will be asked to report on their symptoms prior to intubation, after intubation on the day of discharge, 24 hours after intubation, 48 hours after intubation, and 1 week after intubation.

[Time Frame: Baseline to 1 week after intervention]

4. Pain in the mouth on a scale from 0 (no mouth pain) to 10 (worst possible mouth pain). Subjects will indicate whether they are experiencing mouth pain on a questionnaire. If they indicate 'yes' they will be asked to mark the severity of their symptoms on a scale ranging from 0 (no mouth pain) to 10 (worst possible mouth pain). Participants will be asked to report on their symptoms prior to intubation, after intubation on the day of discharge, 24 hours after intubation, 48 hours after intubation, and 1 week after intubation.

[Time Frame: Baseline to 1 week after intervention]

5. Difficulty talking on a scale from 0 (no difficulty talking) to 10 (complete inability to talk). Subjects will indicate whether they are experiencing difficulty talking on a questionnaire. If they indicate 'yes' they will be asked to mark the severity of their symptoms on a scale ranging from 0 (no difficulty talking) to 10 (complete inability to talk). Participants will be asked to report on their symptoms prior to intubation, after intubation on the day of discharge, 24 hours after intubation, 48 hours after intubation, and 1 week after intubation.

[Time Frame: Baseline to 1 week after intervention]

6. Pain in the neck/chest on scale from 0 (no neck/chest pain) to 10 (worst possible neck/chest pain). Subjects will indicate whether they are experiencing pain in the anterior or low region of the neck and/or chest on a questionnaire. If they indicate 'yes' they will be asked to mark the severity of their symptoms on a scale ranging from 0 (no neck/chest pain) to 10 (worst possible neck/chest pain). Participants will be asked to report on their symptoms prior to intubation, after intubation on the day of discharge, 24 hours after intubation, 48 hours after intubation, and 1 week after intubation.

[Time Frame: Baseline to 1 week after intervention]

Eligibility:

Minimum Age:	18 Years
Maximum Age:	
Sex:	All
Gender Based:	No
Accepts Healthy Volunteers:	Yes
Criteria:	
Inclusion Criteria:
 
• Patient undergoing general endotracheal anesthesia with an endotracheal tube

	
 Patient is not undergoing a procedure in the head and neck region 
Exclusion Criteria:
 
 Patient with pre-existing severe sore throat, voice change, or trouble swallowing Patient undergoing surgery in the head and neck region
--	--

Statistical Analysis Plan

Our statistical plan is outlined below.

• • **Null Hypothesis:**

NH1) Reducing the force on the vocal cords will not change the laryngeal symptoms in participants who underwent Endotracheal Intubation

NH2) Reducing the force on the vocal cords will not change the duration of laryngeal symptoms in participants who underwent Endotracheal Intubation

• • **Alternate Hypothesis:**

AH1) Reducing the force on the vocal cords will change the laryngeal symptoms in participants who underwent Endotracheal Intubation

AH2) Reducing the force on the vocal cords will change the duration of laryngeal symptoms in participants who underwent Endotracheal Intubation

We will use IBM SPSS Statistics, version 28.0.1.1 (14). Student's t-test will be used to compare symptom severity at each time point while Pearson's chi-square test will be used to compare the incidence of throat symptoms across groups. Multiple regression analysis will be used to evaluate demographic and anesthesia variables as predictors of throat symptoms. The odds ratio (OR) and their 95% confidence interval (CI) will be reported for each covariate included in the model. The level of significance (p) to be considered is 0.05.

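### Does it matter that the first post-operative survey is tied to recovery in one place and to discharge in another?

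*Combined protocol and SAP*

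**What the plan says.** The Description sets the first post-operative survey by recovery: "The same survey will be administered after the procedure when the participants are awake and alert ('Day 0". The later surveys follow at "24 hours ('Day 1'), 48 hours ('Day 2'), and 1 week ('Day 7') after the procedure".

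Primary outcomes 1 to 6 each repeat a different form of words. After the pre-intubation survey, symptoms are reported "after intubation on the day of discharge, 24 hours after intubation, 48 hours after intubation, and 1 week after intubation". Here the first survey depends on discharge, and the later ones are counted from intubation.

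The population is "100 subjects who will be intubated for already planned surgeries". The main inclusion criterion is "Patient undergoing general endotracheal anesthesia with an endotracheal tube". The exclusions concern head and neck surgery and severe pre-existing symptoms; length of stay is not mentioned. Under Study Design, enrolment is given as 100, actual.

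In the Statistical Analysis Plan, "Student's t-test will be used to compare symptom severity at each time point", so the first post-operative survey has its own test for each outcome.

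**The concern.** Recovery from anesthesia and discharge from hospital are different events, and nothing in the documents equates them. For a patient who goes home on the day of surgery they are hours apart. For a patient who stays one or more nights they fall on different days.

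If the discharge wording was followed and some patients stayed, the first time point would mix scores from different stages of recovery, and its t-tests would be harder to interpret. The time origin also differs (procedure against intubation), which touches the 24-hour, 48-hour and one-week surveys of every patient. The second pair of hypotheses concerns the duration of symptoms, so the clock could matter there as well.

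**Working it through.** The plan gives no figure to reproduce here: no length of stay, symptom incidence or SD. The check is a comparison of texts, with simple counts.

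**Side by side**

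| Survey | Description | Primary outcomes 1 to 6 |
|---|---|---|
| 1 | before the procedure | before intubation |
| 2 | on recovery, Day 0 | on the day of discharge |
| 3 | 24 h after procedure, Day 1 | 24 h after intubation |
| 4 | 48 h after procedure, Day 2 | 48 h after intubation |
| 5 | 1 week after procedure, Day 7 | 1 week after intubation |

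There are five surveys in each text, in the same order. The discharge survey comes before the 24-hour survey, and the Description labels its counterpart Day 0. Both features point to a first survey on the day of surgery.

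**Effect of length of stay** (assumed, since the documents give none)

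- No nights: the day of discharge is Day 0, and one survey can satisfy both texts.
- One night: the discharge survey falls near the 24-hour survey. It need not fall at or after it. A patient intubated in the afternoon and discharged the next morning is surveyed before 24 hours, and the listed order holds.
- Two nights: it falls near the 48-hour survey.
- More than two nights: it falls after the 48-hour survey, contrary to the order in which the outcome text lists the surveys.

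The first-survey texts therefore diverge for any overnight stay.

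**Share of first-survey scores affected.** Let k be the number of patients first surveyed after the day of surgery, with all 100 giving a first score. The share is k/100. For assumed k = 0, 5 and 20 it is 0%, 5% and 20%. This only restates k; it does not estimate it.

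**Comparisons touched.** All six outcomes carry the same timing words. With four post-operative surveys there are 6 × 4 = 24 severity tests: 6 × 1 = 6 at the first survey and 6 × 3 = 18 later. The Description's symptom list, "a sore throat, throat pain, oral pain, difficulty speaking, difficulty swallowing, changes in their voice, pain while speaking, and pain while swallowing", has no counterpart to outcome 6, "Pain in the neck/chest on scale from 0 (no neck/chest pain) to 10 (worst possible neck/chest pain". Counting only the five matched items gives 5 × 4 = 20 (5 first, 15 later). That is not an upper bound, because outcome 6 shares the timing wording and the chi-square tests of incidence come on top. The missing item is a separate discrepancy.

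**Later surveys.** The shift between the two origins is about the procedure length. The protocol records total procedure time, so the approximate shift can be derived for each patient.

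**Between-arm effect.** Either schedule is the same in both arms. Randomization balances length of stay in expectation, so a mixture of survey times at the first time point enters both arms alike unless the device itself changes when patients go home. The documents give no sign of that.

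**The case for a change.** The strongest case for acting is that the documents never say everyone went home on the day of surgery. Planned surgery under general endotracheal anesthesia includes operations with a hospital stay, and the first time point has its own test. If some first scores came from a later day, a reader could not tell what stage of recovery that test describes. Aligning the wording costs almost nothing.

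Part of this stands. The inconsistency is genuine, and the number of patients affected cannot be recovered from the documents. The origin difference also exists whether or not anyone stayed overnight.

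The case weakens at the next step. Harm at the first time point needs two conditions, neither shown: that patients stayed overnight, and that staff followed the discharge wording rather than the recovery rule. Even then the result is a less sharply defined time point, not a biased comparison. Redefining the first survey by time since surgery would replace an event-based rule that the protocol chose, after the data were collected. A sensitivity analysis without late first surveys would select on length of stay, which arises after randomization, and could create a comparability problem where none has been shown.

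**Conclusion.** The mismatch is real but minor, and the plan need not change. The natural joint reading is a first survey on the day of surgery, once the participant has recovered, followed by surveys at one day, two days and one week. An analyst can work from that reading, check it against survey dates where these were recorded, and describe the timing in the report as a matter of course.

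The size is bounded only by assumption: k% of first-survey scores, with k unknown, and a shift of about one procedure length at the later surveys. No between-arm bias, power loss or wrong figure follows from the text.

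This conclusion rests on two assumptions: that one schedule was applied to both arms, and that the device did not alter the time of discharge. If many patients were in fact first surveyed days after surgery, the first time point would need careful description, but the later surveys and the randomized comparison would remain usable.

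### Six primary symptom scores are tested at four post-operative times at one unadjusted 0.05, with no rule for rejecting NH1, so the false positive rate of the main claim is undefined

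*Combined protocol and SAP*

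**What the plan says.** Under Outcome Measures, one heading, "Primary Outcome Measure", covers six numbered 0–10 scores: sore throat, voice change, difficulty swallowing, mouth pain, difficulty talking and neck/chest pain. There is no secondary list. Each score has a time frame running from baseline to 1 week, with post-operative reports "after intubation on the day of discharge, 24 hours after intubation, 48 hours after intubation, and 1 week after intubation".

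The Statistical Analysis Plan states NH1 as "Reducing the force on the vocal cords will not change the laryngeal symptoms in participants who underwent Endotracheal Intubation". A second hypothesis concerns duration: "Reducing the force on the vocal cords will not change the duration of laryngeal symptoms".

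On methods it says "Student's t-test will be used to compare symptom severity at each time point while Pearson's chi-square test will be used", the chi-square test being used to "compare the incidence of throat symptoms across groups". It closes with "The level of significance (p) to be considered is 0.05". It gives no adjustment, testing order, composite or global test, and no statement of which results would reject NH1.

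Two details leave the set of tests open:

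- The survey in the Study Protocol, Description, has eight items and does not include neck/chest pain, which is primary outcome 6.
- The Description places the first post-operative survey differently: "The same survey will be administered after the procedure when the participants are awake and alert".

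**The concern.** NH1 is one hypothesis, but many p-values bear on it and nothing says which of them decides it. The 0.05 is therefore the error rate of each test, not of the trial's conclusion. A report could present one significant symptom at one time as evidence against NH1 at the 5% level, and nothing in the plan would contradict it. A stricter rule, adopted later, would be equally consistent with the text. While the rule can be chosen after the results are known, the strength of the main claim cannot be stated.

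**Working it through.** The plan gives no error rate, power or sample size derivation, so there is no figure of its own to reproduce.

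**Inputs from the documents.** Six primary scores and four post-operative times (Outcome Measures); level 0.05, taken as two-sided because the alternative hypothesis only says that symptoms will change (Statistical Analysis Plan); 100 participants (Study Design).

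**Assumed, because the documents give no values.** 50 per arm, the correlations, the symptom incidences and the success rule.

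**Number of severity t-tests.** 6 × 4 = 24 is the direct reading, not a stated count. It is 5 × 4 = 20 if neck/chest pain was not asked, and 8 × 4 = 32 if all eight survey items are tested. Taking each time point to include baseline gives 6 × 5 = 30.

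**Any one significant, independent tests.** The rate is 1 − 0.95^k:

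- k = 20: 0.642
- k = 24: 0.708
- k = 30: 0.785
- k = 32: 0.806

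Fixing one dimension is not enough. Six symptoms at one time give 1 − 0.95^6 = 0.265, and one symptom at four times gives 1 − 0.95^4 = 0.185.

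**Any one significant, correlated scores.** Trials were simulated with no effect, and a no answer scored as 0. Latent severities had correlation r between symptoms and r between times (product form). Assumed incidences over the four times were A 50/40/25/8% and B 30/25/15/5%. Rates for any of 24 t-tests (4,000 trials per setting):

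| Latent r | A | B |
|---|---|---|
| 0.15 | 67.6% | 64.4% |
| 0.3 | 66.0% | 62.9% |
| 0.5 | 59.5% | 56.9% |
| 0.7 | 46.7% | 46.4% |
| 0.8 | 38.2% | 38.3% |
| 0.9 | 28.1% | 27.9% |
| 0.95 | 20.7% | 20.0% |
| 0.98 | 18.1% | 16.6% |

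These correlations are latent, and correlations between the recorded scores are lower: latent 0.5 corresponds to about 0.30–0.37, and latent 0.7 to about 0.49–0.57. Correlating the 24 test statistics directly gives 64% at 0.3, 53% at 0.5, 38% at 0.7 and 19% at 0.9.

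**Other families.** A second run (3,000 trials per setting, latent r from 0.98 to 0.15) gave, for any one significant:

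- 24 t-tests alone: 15–67%
- 20 t-tests: 15–61%
- 32 t-tests: 17–78%
- 24 t-tests plus one overall chi-square: 18–67%
- 24 t-tests plus one chi-square per symptom: 22–74%
- 24 t-tests plus 24 chi-squares: 32–83%

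**All 24 significant.** At most 0.5% in the simulated trials. The largest value in any calculation was 0.7%, with all 24 test statistics equally correlated at 0.9.

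**Check of the remedy, no effect.** Testing each symptom's average over the four times at 0.05/6 = 0.0083 gave a family-wise rate of 1.1–5.0%. Five symptoms at 0.05/5 = 0.01 gave 1.6–4.8%. One lead symptom at one time at 0.05 gave 4.4–5.5%, which is 5% within simulation error.

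**The case against.** The strongest reply is that the large percentages belong to a rule the plan never states. The plan does not say that any single significant test suffices, and 24 is inferred from a sentence that neither names the six scores nor restricts itself to post-operative times. Overlapping throat symptoms, repeated in the same patients, are also likely to be well correlated, so the upper end of the range is the less plausible end. All of this is fair. It limits how far any one percentage can be relied on, but it does not supply the missing rule. Even at latent correlation 0.98 the any-one rate was 15–18%, about three times the stated level or more.

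A second reply is that averaging over time is one preference among several and can miss a short-lived effect. That also stands. The defect is the absent rule, and naming one lead test would cure it too.

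Third, the two descriptions of the first assessment may coincide for patients who go home the same day. This is an ambiguity to settle, not a proven contradiction.

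Finally, Study Design lists the study as closed and the enrollment as actual, so a prospective repair may no longer be possible. That changes the form of the remedy, not the need for one.

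**Conclusion.** The concern holds and must be fixed. The plan does not determine the false positive rate of its main claim. Depending on a rule still to be chosen, that rate runs from below 1% (all 24 tests significant) to about 15–68% in simulated trials (any one of 24 significant), or 71% if the tests were independent. That the rate is undefined follows from the text alone. The percentages rest on the assumed success rule, correlations, incidences and equal arms. Every any-one scenario examined was well above 5%.

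**What to change.** **Primary analysis.** Define one test per primary symptom, for example the baseline-adjusted average difference over the four post-operative assessments from a repeated-measures model. Apply Holm over the primary symptoms at a two-sided family-wise 0.05. State that NH1 is rejected if at least one symptom is significant after Holm, and that the claim is limited to those symptoms. An acceptable alternative is one lead symptom at one lead time, chosen without sight of results by arm and tested at 0.05.

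**Settle the family.** Say whether neck/chest pain was collected. If it was not, report and explain the omission and use five symptoms. Say which first post-operative assessment is meant. Report single time points and incidence comparisons as estimates with 95% confidence intervals, labelled secondary. NH2 has no named test: either define one duration measure and add it to the Holm family, or label it secondary.

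**Timing.** Fix and date the choice before results by arm are seen. If they have been seen, report all primary symptoms with adjusted p-values and label the rest exploratory.

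**Cost.** No new patients or data, but less power. Noncentral t with 50 per arm (noncentrality d × √(50/2) = 5d, 98 degrees of freedom) gives:

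| Level | d at 80% power | Power at d = 0.5 |
|---|---|---|
| 0.05 (single test) | 0.57 | 70% |
| 0.05/5 | 0.70 | 45% |
| 0.05/6 | 0.71 | 43% |
| 0.05/7 (six plus NH2) | 0.72 | 41% |

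A 40/60 split moves the 0.05 and 0.05/6 values of d only to 0.58 and 0.72. The table compares levels on one scale; the SD of a baseline-adjusted average differs from that of a single-time score.

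Averaging also dilutes a brief effect. A simulation without baseline adjustment (incidence A, latent r 0.3–0.7) put an assumed 0.6 latent SD shift in one of six symptoms. The averaged analysis at 0.05/6 had 52–74% power if the shift lasted all four times and 23–35% if it was confined to the first two. A lead symptom tested at the first time had 66–70% either way, but only if the affected symptom was the one named. The per-time estimates would still show a short-lived effect.

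### The post-operative severity tests do not adjust for the pre-intubation score of the same symptom, and the incidence test does not say whether a pre-existing symptom counts as an event

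*Combined protocol and SAP*

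**What the plan says.** **Baseline is collected.** The Study Protocol, Description, says that before the procedure "the investigators will survey the participants to get a baseline for any pre-existing laryngeal symptoms". The same survey is repeated on Day 0, 1, 2 and 7, and for a patient who answers no, "this will be considered a score of 0 for the respective outcome variable". Under Primary Outcome Measure, each of the six symptoms carries the statement "Participants will be asked to report on their symptoms prior to intubation, after intubation on the day of discharge", and each time frame starts at baseline.

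**The analysis does not mention it.** The Statistical Analysis Plan says a Student's "t-test will be used to compare symptom severity at each time point", and that "Pearson's chi-square test will be used to compare the incidence of throat symptoms across groups". The only model is described as "Multiple regression analysis will be used to evaluate demographic and anesthesia variables as predictors of throat symptoms". It names neither study arm nor baseline symptom. The plan contains no change score, baseline covariate, baseline stratification or new-onset rule.

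**Patients with symptoms can enter.** The exclusion criteria cover pre-existing severe sore throat, voice change and trouble swallowing. They do not cover mouth pain, difficulty talking or neck/chest pain, nor a sore throat that is not severe.

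**The item lists differ.** The Description's survey items are "sore throat, throat pain, oral pain, difficulty speaking, difficulty swallowing, changes in their voice, pain while speaking, and pain while swallowing". None is neck or chest pain, yet neck/chest pain is the sixth primary outcome and is said there to be reported before intubation.

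**The concern.** A patient's score before surgery may predict the score afterwards. An unadjusted post-operative comparison leaves that variation in the error term, and it carries into the result any baseline difference that arose by chance between two arms of about 50.

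The incidence question is one of definition. A patient with a mild sore throat before surgery and the same sore throat on Day 1 is an event if incidence means any yes answer, and is not an event if it means new onset. The survey's stated purpose points to new onset, but the analysis section does not say so. Two analysts following the text could count this patient differently. If such patients are counted, they add about equally to both arms and dilute the contrast.

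**Working it through.** **Inputs.** From the documents: 100 patients, two arms, significance level 0.05. Assumed: 50 per arm, two-sided testing, effect sizes, the baseline-to-follow-up correlation (rho), baseline prevalence and persistence. The plan states no power figure, so there is none to reproduce.

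**Severity, 0.5 SD effect.** The t-test noncentrality is 0.5 × √(50/2) = 2.5. With 98 degrees of freedom, power is 69.7%. ANCOVA multiplies the variance by (1 − rho²), so the noncentrality becomes 2.5/√(1 − rho²).

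| rho | Noncentrality | Power | Equivalent unadjusted N = 100/(1 − rho²) |
|---|---|---|---|
| 0 | 2.500 | 69.7% | 100 |
| 0.1 | 2.513 | 70.1% | 101 |
| 0.24 | 2.575 | 72.2% | 106 |
| 0.5 | 2.887 | 81.5% | 133 |

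These figures ignore the small cost of estimating the slope, an expected variance factor of about 1 + 1/96 and one degree of freedom. With that cost, power is 69.7%, 71.8% and 81.1% at rho 0.1, 0.24 and 0.5. At rho 0.1 the gain is therefore nil: 0.99 × 1.0104 = 1.0003.

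**Severity under the trial's own scoring.** This simulation (40,000 runs) scores a no as 0. New onset is 50% v 25%, with scores 1-8. The post-operative score is the larger of any persisting baseline score and any new score.

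| Baseline prevalence and scores | Persistence | rho | t-test | ANCOVA |
|---|---|---|---|---|
| 10%, scores 1-3 | all | 0.17 | 56.8% | 58.0% |
| 10%, scores 1-3 | 70% | 0.12 | 57.6% | 58.1% |
| 20%, scores 1-6 | all | 0.44 | 46.5% | 54.9% |
| 20%, scores 1-6 | 70% | 0.31 | 49.9% | 54.0% |

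**Incidence.** Power (%) from 400,000 runs per cell. Each cell gives: chi-square counting every yes / Mantel-Haenszel stratified by baseline answer, without continuity correction / chi-square among patients free of the symptom at baseline. Patients whose baseline symptom does not persist carry their arm's new-onset risk.

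| New onset, persistence | 5% prevalence | 10% | 20% |
|---|---|---|---|
| 50 v 25, all | 69.4 / 72.0 / 72.4 | 64.5 / 69.6 / 70.0 | 54.3 / 64.3 / 64.8 |
| 50 v 25, 70% | 71.0 / 72.1 / 72.4 | 67.3 / 69.4 / 70.0 | 60.4 / 64.2 / 64.9 |
| 40 v 20, all | 52.3 / 57.4 / 57.7 | 46.5 / 54.9 / 55.3 | 38.2 / 50.0 / 50.5 |
| 40 v 20, 70% | 54.4 / 57.0 / 57.7 | 49.8 / 54.2 / 55.4 | 42.9 / 48.6 / 50.4 |
| 60 v 35, all | 68.9 / 68.8 / 69.3 | 64.3 / 66.8 / 67.3 | 54.4 / 61.4 / 61.9 |
| 60 v 35, 70% | 70.3 / 69.2 / 69.3 | 67.0 / 67.1 / 67.1 | 60.4 / 62.3 / 61.9 |

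Against counting every yes, stratifying changes power by −1.1 to +11.8 points. The baseline-free chi-square is within 2 points of the stratified test throughout. It is ahead in 16 of 18 cells, level in one and behind in one. The continuity-corrected Mantel-Haenszel test has less power than counting every yes in 16 of 18 cells.

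**Chance imbalance.** For severity, the 95% limit of the baseline difference is 1.96 × √(2/50) = 0.39 SD, which shifts the unadjusted difference by rho × 0.39: 0.04, 0.09 and 0.20 SD at rho 0.1, 0.24 and 0.5. For incidence at 10% prevalence, two Binomial(50, 0.10) counts differ by 5 or more with probability 13.1%. Given 8 v 3 and no device effect (37.5% new onset in both arms), counting every yes rejects in 8.4% of trials (all persist) or 6.8% (70% persist). The stratified test rejects in 4.5% or 4.9%.

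**The case against.** **The tests are valid.** This stands. A reader might infer that the unadjusted comparisons are biased or have the wrong error rate. They do not: the 8 v 3 rates are conditional on one unfavourable draw. Averaged over all randomisations at 10% prevalence with every symptom persisting, counting every yes rejects in about 5.5% of null trials and the stratified test in 5.0%.

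**Incidence may already mean new onset.** This also stands, and it limits the point. On that reading the planned chi-square already uses the baseline answer. It would be tempting to claim up to 12 points of lost power, but that figure needs three things at once: pre-existing symptoms counted as events, 20% prevalence and full persistence. The documents establish none of them. What remains is that the definition is not written down.

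**The t-test at each time point may include baseline.** It may, so one cannot say that the plan makes no use of the baseline answers. A baseline test would still not adjust the later comparisons.

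**Some baselines will hardly vary.** This stands in part. The voice outcome is defined against the patient's usual voice, so most baseline scores should be near 0. The exclusion can also be read so that the word severe applies only to sore throat, which would exclude any voice change or swallowing trouble. For those symptoms adjustment may gain little. Mouth pain, difficulty talking and non-severe sore throat are unaffected by this argument.

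**Conclusion.** The point holds as an improvement worth making, not as an error in the plan. Two omissions are plain in the text: the post-operative severity comparison has no baseline adjustment, and incidence is undefined for a patient already symptomatic before surgery. The regression repairs neither, because it names neither arm nor baseline symptom.

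The size is uncertain because every input beyond 100 patients and the 0.05 level is assumed. For severity, the gain runs from almost nothing at rho 0.1 to about 12 points at rho 0.5. If most baseline scores are 0, the lower end is more likely. For incidence, there is a gain only if pre-existing symptoms would otherwise be counted. A baseline is certain for five of the six primary symptoms. For neck/chest pain the two lists conflict.

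**What to change.** 1. **Severity.** Replace the t-test at each post-operative visit (Day 0, 1, 2 and 7) with ANCOVA, with arm and the baseline score of the same symptom as terms. Report the adjusted arm difference with its 95% CI. Where the baseline score is nearly constant, as is likely for voice change, the unadjusted result may be reported. Make that decision from the baseline scores alone.
2. **Incidence.** Write down one definition before unblinding. Either use new onset among patients free of that symptom at baseline, by the planned chi-square, or keep all randomised patients and stratify by the baseline yes/no answer with the Mantel-Haenszel test without continuity correction. Do not choose between them from the outcome data.
3. **Neck/chest pain.** Reconcile the Description's survey list with the sixth primary outcome. If no baseline answer exists, analyse that outcome unadjusted and say so.
4. **Timing.** Study Design lists enrollment of 100 as actual, and says the investigator knows the arm while data analysis is blinded. Date the change before arm labels are joined to outcomes, or label the analysis post hoc.

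The cost is SAP wording and a few lines of SPSS code. No new data are needed for the five symptoms that appear in both lists.
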